8.6 Definition of secondary endpoints

Secondary endpoints are defined in 3.2

8.6.1 Definition of Overdiagnosis

Overdiagnosed breast cancer cases are defined as cancers that would never have been diagnosed, if women had not been screened. Differential overdiagnosis can be measured comparing the cumulative incidence of breast cancer from recruitment to a reasonably long period after the end of the intervention, i.e. longer than the expected sejour time of screen-detected cancers. In this study the two groups will be monitored for breast cancer incidence for 10- and 15-years after the end of the intervention.

The overall excess overdiagnosis with risk-based screening compared to standard protocol will be estimated from the trial. Different lead time models will be applied to obtain a range of model-based estimates of overdiagnosis. A microsimulation model will be calibrated to the trial population for overdiagnosis estimates and cost and cost-effectiveness evaluation.

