LONG TERM DATA COLLECTION FOR THE EVALUATION OF INCIDENCE AND BREAST CANCER SPECIFIC MORTALITY VIA INTERROGATION OF DATA COUNTRY-SPECIFIC HEALTH INSURANCE AND SCREENING STRUCTURES DATA BASES (NOT INTERVENTIONAL, NOT PART OF THE STUDY FOLLOW-UP): UP TO 15-YEARS FROM STUDY ENTRY

DURATION UNTIL PRIMARY ENDPOINT EVALUATION (INCLUSION + FOLLOW-UP) : 6.5 YEARS

H) STUDY SCHEME/OUTLINE

I) SCHEDULE OF ACTIVITIES (SOA)

VISITS	Who will record the data into the web-platform	Baseline	Risk-based screening arm	Follow-up			
				NA	NA	NA	NA
Visits n°		Visit (V0)	V1	M12 V0 + 12 +/- 6 months	M24 V0 + 24 +/- 6 months	M36 V0 + 36 +/- 6 months	M48 V0 + 48 +/- 6 months
Visit / Follow up timepoints Dates		D0	V0 + 8-12 weeks				
Type of visit		physical	physical or telephone call	On-line	On-line	On-line	On-line
Inclusion/non-inclusion criteria	investigator	X					
Signed informed consent form	Investigator/Woman	X					
Baseline mammogram (if applicable)		X*					
Minimal medical data	investigator	X					
Randomization	investigator	X					
Medical history	investigator/Woman	X					
Result of risk score (only for risk-based screening)	investigator		X				
Study visit	NA	X [#]	X [§]				
Study mammogram	NA	(X) [£]	(X) [£]	(X) [£]	(X) [£]	(X) [£]	(X) [£]
BIOLOGICAL TEST (only for women who will be randomized in the risk-based screening arm)							
Saliva test		X					
QUESTIONNAIRES							
1. STAI short form (state anxiety)	Woman	X	X	X			X
2. Comprehension questionnaire	Woman	X	X				X
3. Information seeking-behavior questionnaire	Woman		X				X
4. Quality of life (EQ-5D)	Woman	X					X
5. Satisfaction	Woman			X			X
6. Socio-demographic and economic status questionnaire	Woman	X					X
FOLLOW-UP DATA							
Mammogram yes/no + results	Woman/ OBSS or national security social			X	X	X	X
Breast US (or ABUS) yes/no + results	Woman/ OBSS or national security social			X	X	X	X
Breast MRI yes/no + results	Woman/ OBSS or national security social			X	X	X	X
Breast biopsy or surgery + result and date	Woman/ OBSS or national security social			X	X	X	X
Breast cancer yes/no + date	Woman/ OBSS or national security social			X	X	X	X
Other major medical problem yes/no + date	Woman/ OBSS or national security social			X	X	X	X

* Reference mammograms up to 2 year prior to inclusion are accepted

For woman who will have the standard of care screening program

§ For woman who will have the risk-based screening program

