1.1.26 Long-term follow-up in MyPeBS

Although the intervention in MyPeBS will only last for 4 years, part of its consequences could last longer, especially in so-identified high risk women, who may continue both the more intense screening they have been proposed, as well as risk-reducing strategies they were advised on. It is therefore crucial we can have access to long-term stage II and higher breast cancer incidence, as well as long-term breast cancer specific mortality.

We intend to retrieve such data at 10- and 15-years from study entry.

This will allow first to identify the long-term effect of risk-based screening program as compared to standard screening, but also to refine long-term risk assessment and risk scores, in this very carefully annotated cohort.

To this end, we will not be able to retrieve data from participants nor investigators, who will not be asked any more participation after 4 years. We have therefore organised towards being able to cross our database with national health system databases and national security insurance systems databases, in each country.

1.1.27 Long-term additional research developments based on MyPeBS' database, rationale for collection of images and saliva DNA

Finally if risk-based screening is demonstrated as more efficient and more acceptable for women than standard screening, it will become crucial that risk identification can be further refined in the future.

This refinement would also dramatically serve prevention programs in the future.

It is highly likely that germline DNA can contribute to such risk identification refinement in the future, not only through the discovery of new SNPs, but also to avenues open by the potential of whole genome sequencing, and epigenetic assessments, for example.

Beside this, mammographic and other images also are of great promise for the purpose of risk identification.

For these reasons, we have organised towards storing saliva DNA of women who will consent to, for the purpose of additional research as described. We also wish to collect and store mammographic images of a maximum of participants, provided they have given their consent for this, as well. The informed consent form has been written accordingly.

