3. STUDY DESIGN AND ENDPOINTS

3.1 Description of the Study Design

MyPeBS is a European randomized open-label, multicentric, study assessing the effectiveness of a risk-based breast cancer screening strategy (using clinical risk score and polymorphisms) compared to the standard of care in terms of detection of high-risk cancers (**according to current national guidelines in each country**), in detecting stage 2 + breast cancers.

Our overall objective is to compare the effectiveness of two Breast Cancer Screening strategies:

[figure not shown]
- **Standard strategy:** Current standard of care in participating countries where women are invited to a common schedule of screening mammograms performed once every 2-3 years starting from ages 40-50 up to ages 69-70, while the already identified very high risks individuals (at most 5%) have more intense personalized follow-up;

- **Risk-based strategy:** Extension of the personalized screening strategy, in which women are invited to radiological examinations scheduled according to their risk of developing breast cancer and to an individually-defined plan, for the whole population.

Our primary hypothesis is that risk-based screening will be **non-inferior** in terms of overall stage 2+ breast cancer incidence. We hypothesize it should also be **superior (decreased incidence of stage 2+ breast cancer); equally or more cost-effective;** but more acceptable (resulting in a wider coverage and a better compliance) **than standard screening.**

Women will be differentially screened for 4 years and then, after an end-of-study mammogram, they will return to the routine screening practice. The main endpoint is measured at the end of the four years of intervention. Furthermore follow-up data will be collected for 15 years from study entry of long-term cumulative breast cancer incidence and breast cancer specific survival.

General design

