3.2.2 Secondary endpoint(s)

SECONDARY ENDPOINT(S): (All at 4 years/during intervention period unless otherwise indicated):

1. Rates of false positive imaging findings and benign biopsies in each study arm
 - False positive imaging findings include BI-RADS-ACR 3, 4 and 5 (or equivalent) lesions identified on screening images and leading to the need of additional images (US, MRI...), later control or breast biopsy
 - Benign biopsies include any percutaneous or surgical breast diagnostic procedure aimed at identifying the nature of a breast image
2. Socio-psychological assessments at baseline, and then at 1 and 4 years including evaluation of: comprehension of information, acceptance of proposed screening strategy, observance, persistence, anxiety, distress, satisfaction, decisional regret (see questionnaires in table 1)
3. Crude costs, comparison of cost-effectiveness, and budget impact of each strategy
 - Crude costs are defined as full real costs per stage 2 cancer diagnosis in each arm
 - The cost-effectiveness of mammographic screening will be calculated by comparing estimated life-years and costs of breast cancer in each arm
4. Incidence of stage-specific breast cancer in each arm (including DCIS)
5. Estimates of overdiagnosis and overtreatment rates in each study arm
 - Overdiagnosed breast cancer cases are defined as cancers that would never have been diagnosed, if women had not been screened. Differential overdiagnosis can be measured comparing the cumulative incidence of breast cancer from recruitment to a reasonably long period after the end of the study intervention, i.e. longer than the expected sejour time of screen-detected cancers. Breast cancer incidence rates in each arm will be determined approximately 10 - 15 years after the end of the interventional period of the study via interrogation of databases from national health insurances and/or organized breast screening structures.
6. Rate of false negative images and interval cancers in each arm
 - False negative images: in case of diagnosis of breast cancer in women whose last screening images (including mammogram +/- US and MRI) were considered as Breast Imaging- Reporting and Data System 1 or 2 (BI-RADS 1 or 2) at 6 months maximum before diagnosis

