11.1.2 Overall Data collection rules

Regarding the data collection, the general principles are described in the Table below:

- A minimal information is entered by the investigator and women at the baseline
- A web-based yearly update of personal data will be self-entered in the system by all participating women upon yearly invitation (email, SMS, other)
- Results of images will be both self-declared and retrieved through the screening coordination centers for the purpose of the main end point. For secondary end-point (economical analysis) additional data will be collected from national insurance system.
- An out-of-study mammogram will be mandatory at 4 years for all women included

Type of data	Mode of collection	Comment
Baseline data	Web-platform site	Filled by investigator and women
Randomization	Web-platform site	
Initial risk assessment	Web-platform site	Filled by investigator and/or women for some country
Questionnaires	Web-platform site	Filled by participants
Update of personal participants data	Web-platform site	Filled by participants

Results of all imaging examinations	Web-platform site	Filled by women and screening centers
Results of biopsies or surgeries (benign)	Web-platform site	Filled by women and screening centers
Cancer events	Web-platform site	Filled by women, investigators, filled /imported from screening centers and imported from national security insurance database

All women will be followed for 4 years from randomization for the inferential analysis of the trial.

Long-term breast cancer specific mortality data will be retrieved in each country through regularly (if possible) and otherwise at the end of the trial crossing with national databases (national health insurance databases and national epidemiological and statistical databases) in concerted, pre-planned, anonymous fashion.

A long term data collection for the evaluation of incidence and breast cancer specific mortality via interrogation of data country-specific health insurance and screening structures data bases will be performed up to 15 years from study entry of the participants.

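### Section 8.6.1 promises incidence to 15 years after the intervention for overdiagnosis, but data collection ends 15 years from entry, at most 11 years after the intervention

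*Protocol*

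**What the plan says.** Two time origins are used for the same long-term incidence data.

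**Counted from the end of the intervention.** Section 8.6.1 defines differential overdiagnosis as a comparison of cumulative incidence, counted from recruitment, over a period that continues long enough after the intervention to exceed the expected sojourn time of screen-detected cancers. It then says the arms will be "monitored for breast cancer incidence for 10- and 15-years after the end of the intervention". Secondary endpoint 5, in section 3.2.2 and in the synopsis, uses the same origin more loosely: incidence will be determined "approximately 10 - 15 years after the end of the interventional period of the study".

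**Counted from study entry.** Each description of long-term data collection uses entry:

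- Section 3.1: "Furthermore follow-up data will be collected for 15 years from study entry of long-term cumulative breast cancer incidence". The study description in the synopsis says the same.
- Synopsis, part G (study duration): "UP TO 15-YEARS FROM STUDY ENTRY".
- Section 1.1.26: "We intend to retrieve such data at 10- and 15-years from study entry".
- Section 11.1.2: long-term collection "will be performed up to 15 years from study entry of the participants".

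The length of the intervention is not in doubt. Section 1.1.26 says: "Although the intervention in MyPeBS will only last for 4 years".

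**The concern.** An excess-incidence estimate of overdiagnosis depends on how long both arms are observed after the screening schedules stop differing. While that period is short, cancers that were only brought forward by screening cannot be separated from cancers that would never have surfaced. Section 8.6.1 accepts this by tying the method to a post-intervention period longer than the sojourn time. Years since the end of the intervention are therefore the relevant clock, and years from entry overstate them by the 4 years of differential screening.

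A reader of 8.6.1 would credit the estimate with up to 15 post-intervention years. If the data stop earlier, the protocol describes a property that the design does not have. This matters because the protocol treats overdiagnosis as a screening harm and a safety evaluation (sections 1.1.16, 6.2.1 and 12.2), and fewer overdiagnoses in low-risk women is part of the trial's rationale (section 1).

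**Working it through.** **Inputs**

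- Intervention: 4 years from randomization (sections 1.1.26 and 3.1).
- Limit of long-term collection: 15 years from entry, per participant (section 11.1.2; also the synopsis and section 3.1).
- Planned retrievals: 10 and 15 years from entry (section 1.1.26).
- Stated overdiagnosis horizons: 10 and 15 years after the intervention (section 8.6.1).
- Accrual: 2.5 years (section 8.2.3), used only in step 4.

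**Step 1. Check the time axis on a figure that the protocol gives.** Time to the primary endpoint evaluation = accrual + follow-up = 2.5 + 4 = 6.5 years. This matches the 6.5 years in the synopsis.

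**Step 2. Convert the horizons in 8.6.1 to years from entry.** Years from entry = 4 + years after the intervention.

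| Horizon in 8.6.1 (after intervention) | Needed from entry | Within the 15-year limit? |
|---|---|---|
| 10 years | 4 + 10 = 14 | Yes |
| 15 years | 4 + 15 = 19 | No, short by 19 − 15 = 4 years |

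**Step 3. Convert the planned retrievals to years after the intervention.** Years after the intervention = years from entry − 4.

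| Retrieval (from entry) | Years after intervention |
|---|---|
| 10 years | 10 − 4 = 6 |
| 15 years | 15 − 4 = 11 |

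The pair 10 and 15 in 8.6.1 is not reproduced: the scheduled retrievals give 6 and 11.

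**Step 4. Try the most favourable reading of the limit.** Suppose there were one calendar cut-off, when the last woman enrolled reaches 15 years. The earliest entrants would then have 15 + 2.5 − 4 = 13.5 post-intervention years, still under 15. Section 11.1.2 in any case sets the limit from each participant's own entry.

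**The case against.** **Endpoint 5 can be met.** Section 8.6 refers to section 3.2 for the definitions of secondary endpoints, and item 5 there gives an approximate range of 10 to 15 years. Eleven years lies inside it. This stands: a reader might infer that the overdiagnosis endpoint as a whole cannot be delivered, and the documents do not support that. The part that fails is the 15-year point in 8.6.1; in endpoint 5 only the upper part of the range is out of reach.

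**The 10-year point is not lost.** A reader might also infer that neither horizon in 8.6.1 can be obtained, because neither coincides with a retrieval date. If the linked diagnoses carry dates, the retrieval at 15 years from entry also yields cumulative incidence at 14 years from entry, which is 10 years after the intervention. That the linked records are dated is an assumption, but a reasonable one, since the trial's own schedule of activities records the date of each breast cancer.

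**Inflation of the excess is not shown.** It is tempting to conclude that the shorter horizon inflates the overdiagnosis estimate. The protocol gives no sojourn time, so it cannot be said that 11 years is too short. Both arms are screened, and the risk-based arm intensifies screening for some women and reduces it for others (section 1.1.14). Some women in either arm who had no scheduled screening have a mammogram at 4 years (section 3.1.4), and afterwards both arms return to routine practice. Residual lead time could differ in either direction. Section 8.6.1 also plans several lead-time models and a calibrated microsimulation, so the estimate does not rest on raw excess incidence alone.

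**What these points do not answer.** Modelling does not supply the observed follow-up that 8.6.1 states. The 25-year retention periods in sections 13.6 and 14.2 concern document archiving, not incidence follow-up. An analysis plan can choose its time points but cannot analyse years that are not collected.

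**Conclusion.** Section 8.6.1 is wrong as written on one point. Monitoring to 15 years after the intervention would need 19 years from entry, and the protocol collects data to 15. The longest horizon that the design provides is 11 post-intervention years, 4 fewer than stated. The 10-year point is reachable but unscheduled, and the first retrieval gives 6 post-intervention years.

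This rests on an intervention of 4 years for every woman and on the 15-year limit running from each woman's entry. It does not rest on any assumption about sojourn time. For the same reason it says nothing about whether 11 years is enough, or about the sign or size of any remaining lead-time bias.

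The consequence is limited. Overdiagnosis is one of twelve secondary endpoints and is an estimate for which the protocol states no hypothesis test. The primary endpoint, the sample size and the non-inferiority analysis are unaffected. The correction is still worth making, because the horizon is the feature on which 8.6.1 rests the validity of the comparison.

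**What to change.** 1. **Use one time origin.** Restate 8.6.1 so that cumulative incidence is counted from recruitment and compared up to 15 years from entry, with the equivalent of about 11 years after the intervention given alongside. Use the latest linkage for the overdiagnosis estimate. If a 10-year post-intervention estimate is wanted, say that it will be read at 14 years from entry out of that same linkage, and confirm that the linked diagnoses are dated.
2. **Qualify endpoint 5.** In section 3.2.2 and the synopsis, note that the upper end of the range is limited to about 11 years after the intervention. The endpoint needs no redefinition.
3. **Check the criterion in 8.6.1.** State the expected sojourn time that is being assumed, with its source, and confirm whether 11 years, and the 6 years given by the first retrieval, exceed it.

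The first two items are wording changes; the third needs one sourced figure. The price is a shorter stated horizon. The alternative is to keep 15 post-intervention years and extend database linkage to 19 years from entry. That is a substantive change to data collection, and whether existing consents and linkage agreements would allow it cannot be judged from the protocol text available.

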8.6.2 Definition and methods for other secondary end points

- False positive recalls and rates of benign biopsies will be measured as stipulated by the European Guidelines for Breast cancer screening (<http://www.euref.org/european-guidelines>, and <http://ecibc.jrc.ec.europa.eu/-/european-guidelines-for-breast-cancer-screening-and-diagnosis-the-european-breast-guidelines>)
- Socio-psychological impact of risk-based screening as compared to standard, will be evaluated using validated questionnaires, as largely described in WP5 of the whole project
- Costs and cost-effectiveness will be evaluated as largely described in WP4 of the whole project H2020 (refer to section 1.1.25)
- Underserved women will be defined using both the European Deprivation Index (EDI) and the International Standard Classification of Education (ISCED) scales, both being validated at a European level
- Interval cancer will be defined following the European Commission's definition, as a primary breast cancer, which is diagnosed in a woman who had a screening, test, with/without further assessment, which was negative for malignancy, either:

- before the next invitation to screening, or
 - within a time period equal to a screening interval for a woman who has reached the upper age limit for screening.
- Breast cancer specific survival will be defined according to the DATECAN definition (Gourgou et al)

As planned in the secondary end-points, we will perform joint analyses of MyPeBS with the WISDOM personalized breast cancer screening trial performed in California and the Midwest (PI [name], UCSF). These analyses will be performed after the primary analysis of MyPeBS (scheduled for 2025) and WISDOM (scheduled for 2020). The joint analyses will address two different objectives:

- Estimate the differential effect of stratified screening in terms of decreasing stage 2+ cancers across the two trials
- Joint analysis for long-term disease specific mortality (this will require at least 10- and 15-years of follow-up)

A joint steering committee will be set-up and a statistical analyses plan for the joint analysis using meta-analysis techniques.

9. OVERSIGHT COMMITTEES

MyPeBS project is conducted by a European consortium regrouping 50 major physicians, scientists, healthcare providers and patients' advocates in the field, from 6 countries.

The sponsor of the clinical trial is UNICANCER.

9.1 Clinical trial Steering Committee

In the framework of this clinical study, a Clinical trial Steering Committee (CTSC) will be constituted to oversee all questions regarding the clinical trial as well as the exploitation of the common database (ancillary studies and industrial partnerships).

The clinical trial Steering executive committee will meet physically twice a year (or at least through a teleconference) every months during the set-up and the beginning of the accrual phase to ensure an effective and timely start of the clinical trial. Additional meetings may be organised, as required.

- This committee will be constituted of the coordinator, a representative of the sponsor, the PI of the five countries participating in the trial, 2 representatives of patients, and the task leaders of work package of European project (Methodology, Statistical analysis, genotyping, imaging, quality insurance, risk evaluation)
- The Steering Committee is composed of and working according to the study related CTSC Charter, which will be written, approved and signed by all members before any activity.
- All CTSC members will have to fill and update yearly a conflict of interest statement form, throughout their participation as members of the CTSC.
- The SC is responsible for top-level trial design and management decisions, also in consideration of any DMC recommendations
- The Steering committee will also follow the conduct of this study, assist the sponsor (UNICANCER) in resolving issues and/or questions encountered during the conduct of the trial and will consider, with the sponsor, changes to the protocol as necessary.
- The steering committee will be scientifically responsible for the proper conduct of this study and the interpretation and publication of its results.

- The SC will be responsible for writing the publication plan, revising and authorizing all publications issued from the trial, organization publication agenda.
- It will meet by phone conference every month during the set-up and the beginning of the accrual phase to ensure a effective and timely start of the clinical trial. Meeting schedule will be reduced once accrual is going as planned and during the follow-up phase.
- Two-yearly physical meetings of the SC will be planned throughout the conduct of the study.
- Additional representatives and investigators might be invited to address specific questions as necessary.

